### Tool Revision History

Version Date: 1/31/19

### Summary of Revision Made:

- Changes made to reflect NIH protocol template
- Updated to include R33 phase

**Précis:**

Study Title:

“Pilot Study of Zinc Supplementation and Cardiovascular risk in HIV infection”

**STUDY OBJECTIVES**

**PRIMARY:**

- To replicate findings from R21 and examine whether zinc supplementation will change biomarkers (hs-CRP, sCD14, sTNF-RI, and microbial translocation LBP)
- To examine whether zinc is safe and effective at increasing zinc levels in HIV-infected subjects with zinc deficiency.

**SECONDARY:**

-- To assess the associations between the inflammatory markers (hs-CRP, sCD14, sTNF-R1 and LBP) and insulin resistance and endothelial function.

-To assess the safety and tolerability of zinc supplementation

-To assess the association between changes in zinc levels and insulin resistance and endothelial function

-To assess the association between changes in zinc levels and changes in gut markers of intestinal fatty acid binding protein (I-FABP), and zonulin.

**EXPLORATORY:**

-To assess the association between changes in zinc levels on advanced glycation end (AGE) products accumulated in the skin.

-To assess the association between changes in zinc levels and lipids

**STUDY ENDPOINTS**

**Co-PRIMARY:**

-Changes in markers of inflammation and immune activation: hs-CRP, sCD14, sTNF-RI and microbial translocation LBP

-Changes in zinc levels (before and after supplementation)

**SECONDARY:**

- Metabolic/CVD factors: endothelial function and insulin resistance

-Safety/tolerability:- Tolerance of zinc reported by patients and safety measures will also be assessed (percent of subjects with >Grade 2 adverse events possibly or probably due to study drugs).

--Markers of gut integrity: intestinal fatty acid binding protein (I-FABP), and zonulin.

## EXPLORATORY:

-Advanced glycation end (AGE) products accumulated in the skin.

-Lipids

-To assess the association between changes in zinc levels and lipids

## Design and Outcomes:

This is a double-blind randomized placebo-controlled trial assessing the effect of zinc supplementation on improving zinc deficiency and risk of HIV-related comorbidities linked to inflammation and assessing its safety and tolerability in HIV deficiency compared to placebo drug in HIV-infected subjects  $\geq 18$  years old, on stable ART (for at least 12 weeks), and with baseline zinc levels  $\leq 0.75$  mg/L in the last 60 days.

Subjects will be evaluated, and data will be collected according to the following schedule:

Evaluation (Weeks)	Screen I	Screen II	Entry	6	12	18	24
Family history of CVD and diabetes		X					X
Framingham and Reynolds Risk Scores			X		X		X
Targeted physical, blood pressure, weight	X	X		X	X	X	X
Anthropometric Measurements	X	X					X
Compliance, safety monitoring				X	X	X	
Smoking, illicit drugs and alcohol status	X				X		X
Dietary and Activity status	X				X		X
Height	X						
Hematology/chemistries	X	X		X	X	X	X
Urine $\beta$ -HCG (women)	X	X		X	X	X	X
Lipoprotein profile			X		X		X
Insulin, glucose, HOMA-IR			X		X		X
Inflammation and immune activation markers			X		X		X
Gut integrity, microbial translocation, intestinal permeability			X		X		X
Oxidative markers			X		X		X
Zinc level	X		X		X		X
Copper level			X				X
EndoPat, AGE testing		X			X		X
Resting Energy Expenditure (REE)	X						X
Cognivue			X				X
Stored plasma, serum and urine	X	X		X	X	X	X
Stored PBMC			X		X		X
Stored Stool		X	X		X		X

**Intervention and Duration:**

The duration of the study will be 24 weeks. Patients will be given zinc gluconate capsules at a dose of 90 mg elemental zinc daily or matching placebo for 24 weeks. No additional follow up will occur after 24 weeks.

**Sample size and population:**

The total sample size is 95 patients, 63 patients will be randomized to two 45 mg (or 90 mg) capsules of zinc gluconate and 32 patients will receive two matching capsules of placebo drug. This study will be conducted at the University Hospitals Cleveland Medical Center. Recruitment will be done at the Special Immunology Unit (SIU) at the University Hospitals Main Campus.

**BACKGROUND:**

It has been estimated by the World Health Organization that nearly two billion subjects may be zinc deficient in the developing countries. This is due to the fact that most of these populations consume mainly bread made of whole wheat flour, which is high in phosphate compound that decreases the absorption of both iron and zinc. The phytate to zinc molar ratio >20 in a diet is unfavorable for zinc absorption and this may lead to zinc deficiency. In the developed countries, zinc deficiency is also prevalent in the elderly population or even in younger subjects with HIV, where up to 30% of non-malnourished subjects were found to be zinc-deficient. Low concentrations of zinc are prevalent in HIV-1-infected male and female drug users as well as other HIV-1-infected cohorts. Such low concentrations of plasma zinc have been linked with disease progression, independent of baseline CD4 cell count, lymphocyte concentrations and age- and calorie-adjusted dietary intake. Of particular importance, low plasma zinc levels have been associated with a threefold increased risk of HIV-1-related death in HIV-1-seropositive drug users.

In mild to moderate deficiency of zinc, the clinical manifestations may include growth retardation in children, rough skin, poor appetite, mental lethargy, delayed wound healing, T cell-mediated immune dysfunction, and neurosensory disorders

Pertinent to this proposal, zinc has anti-inflammatory properties due to NFkB blockade, and is an anti-oxidant agent. Zinc decrease NF- $\kappa$ B activation and its target genes such as TNF- $\alpha$ , IL-1 $\beta$ , and VCAM and increased the gene expression of A20 and PPAR- $\alpha$ , the two zinc finger proteins with anti-inflammatory properties. Thus, zinc decreased the expression of these cytokines and molecules by inhibition of NF- $\kappa$ B activation via A20 and PPAR- $\alpha$  pathways. As such, zinc supplementation has been investigated as immunomodulatory and anti-inflammatory agents

In healthy volunteers who were supplemented with 45 mg elemental zinc daily, a significant decrease in TNF- $\alpha$  and IL-1 $\beta$  messenger RNAs and TNF- $\alpha$  induced NF- $\kappa$ B DNA binding were found in isolated peripheral blood mononuclear cells in comparison to placebo treated subjects. In elderly, zinc supplementation with daily 45 mg elemental zinc as gluconate for 6 months was safe, and led to significant increase in plasma antioxidant power, decrease in

plasma oxidative stress marker, and decrease in the inflammation markers C-reactive protein, IL-6, MCP-1, and VCAM-1. Even more, plasma zinc concentrations were inversely correlated with the changes in plasma levels of hsCRP, MCP-1, and VCAM-1 after the zinc supplementation.

The Recommended Dietary Allowance for zinc (intake of 15 mg zinc/d for men and 12 mg zinc/d women) was established in 1974 for the first time. We will use 90 mg elemental zinc/d as oral supplementation because it has been used safely in non-HIV studies including in elderly individuals for 1 year duration, and at this concentration, no serious adverse events were reported and copper status remained normal. This is important because the only adverse effect of very high doses of oral zinc supplementation for a prolonged duration is copper deficiency.

Zinc sulfate is inexpensive, available over the counter, and has an excellent safety profile. If zinc positively influences the mechanisms postulated to play a role in HIV cardiovascular disease, this affordable treatment would become relevant to millions of people worldwide, not only for people living with HIV but also individuals suffering from other conditions of heightened inflammation such as rheumatoid arthritis, diabetes, or lupus.

#### **RATIONALE:**

Zinc is a dietary supplement with compelling preclinical evidence for potential health benefit that could be expanded not only to the entire HIV population, but also to other inflammatory conditions that share many facets of HIV infection, namely the persistent intestinal barrier dysfunction, monocyte activation and heightened inflammation state. Such diseases include inflammatory bowel diseases, rheumatoid arthritis, diabetes and even obesity in the general population. Our proposal incorporates assessment of defined signatures of biological effects and will provide important mechanistic insights to inform us on the mechanism of action through which zinc may produce clinical benefit, and as such will provide the information necessary to develop a competitive full-scale clinical trial.

This study will focus on subjects with documented zinc deficiency (levels <75 µg/dL) as group most likely to benefit from the zinc supplementation. We also acknowledge that zinc may be beneficial in all HIV subjects, regardless of the plasma zinc level; however initial studies should be done in subjects with low zinc levels as they are more likely to benefit. If we find promising results in these zinc-deficient subjects, future studies will explore other populations such as large scale trials in HIV-positive subjects regardless of zinc levels.

At the dose used, uncommon side effects include nausea, vomiting, and abdominal pain (gastritis). At higher doses and when used for a long periods (years), copper deficiency and related anemia may happen. This is very unlikely since we are only giving 90 mg daily and for up to 24 weeks. Such doses have been shown to be safe even when given for 12 months to elderly frail subjects. In addition, in diseases such as Wilson's disease, zinc is given at a dose of 50 mg three times daily for prolonged durations. We will closely monitor subjects who will receive blood draws for chemistries, hematology and liver enzymes every 6 weeks, and as needed between study visits

## **HYPOTHESIS:**

In HIV-infected subjects on ART with documented zinc deficiency, short term zinc therapy will be safe, effective at increasing zinc levels, and will result in improvement in selected markers of inflammation and microbial translocation.

## **STUDY OBJECTIVES**

### **PRIMARY:**

- To replicate findings from R21 and examine whether zinc supplementation will change biomarkers (hs-CRP, sCD14, sTNF-RI, and LBP)
- To examine whether zinc is safe and effective at increasing zinc levels in HIV-infected subjects with zinc deficiency

### **SECONDARY:**

To assess the associations between the inflammatory markers (hs-CRP, sCD14, sTNF-R1 and LBP) and insulin resistance and endothelial function.

-To assess the safety and tolerability of zinc supplementation

-To assess the association between changes in zinc levels and insulin resistance and endothelial function

-To assess the association between changes in zinc levels and changes in gut markers of intestinal fatty acid binding protein (I-FABP), and zonulin.

### **EXPLORATORY:**

-To assess the association between changes in zinc levels on advanced glycation end (AGE) products accumulated in the skin.

-To assess the association between changes in zinc levels and lipids

## **STUDY ENDPOINTS**

### **Co-PRIMARY:**

--Changes in markers of inflammation and immune activation: hs-CRP, sCD14, sTNF-RI and microbial translocation LBP)

-Changes in zinc levels (before and after supplementation)

### **SECONDARY:**

- Metabolic/CVD factors: endothelial function and insulin resistance

-Safety/tolerability:- Tolerance of zinc reported by patients and safety measures will also be assessed (percent of subject with >Grade 2 adverse events possibly or probably due to study drugs).

--Markers of gut integrity: intestinal fatty acid binding protein (I-FABP), and zonulin.

**EXPLORATORY:**

- Advanced glycation end (AGE) products accumulated in the skin.
- Lipids

**INCLUSION CRITERIA:**

-HIV-1 infection as documented by any licensed ELISA test kit and confirmed by Western blot at any time prior to study entry. HIV-1 culture, HIV-1 antigen, plasma HIV-1 RNA, or a second antibody test by a method other than ELISA is acceptable as an alternative confirmatory test

-Documentation of an HIV-1 RNA level of  $\leq 400$  copies/mL in the last 4 months prior to study entry

-Male or Female age  $\geq 18$  years

-Zinc level  $\leq 0.75$  mg/L *in the last 60 days*

-Receiving a stable antiretroviral regimen for at least the last 12 weeks prior to study entry

-Cumulative duration of antiretrovirals for at least 6 months at study entry

-Provides written informed consent and is capable of reading and comprehending the informed consent

**Non-English-Speaking Subjects:** Subjects who do not understand or speak English will also be eligible for this study. The consent form will be read to those non-English speaking study candidates in their primary language by a translator. A witness (who speaks English and the study subject's language) will be present to confirm the consent process has taken place. Both the witness and person conducting the consent process will sign and date the consent. The investigator obtaining consent will ask the study candidate via the translator to reiterate what will be required from him/her, risks and benefits, and his/her rights as a participant to ensure their full understanding of the study.

-Have no plans to alter antiretroviral therapy, diet or exercise or initiate structured/strategic antiretroviral treatment interruptions.

-Able to swallow pills.

-No diarrhea or nausea/vomiting for the last month.

-All women of child-bearing potential (WOCBP) must have a negative serum or urine pregnancy test (minimum sensitivity 25 IU/L or equivalent units of HCG) within 72 hours prior to start of study medication. WOCBP is defined as any female who has experienced menarche and who

has not undergone successful surgical sterilization (hysterectomy, bilateral tubal ligation, or bilateral oophorectomy), who is not postmenopausal (defined as amenorrhea for 12 consecutive months), or is on hormone replacement therapy (HRT) with documented plasma follicle-stimulating hormone level 35mLU/mL. Women who are using oral, implanted, or injectable contraceptive hormones or mechanical products such as an intrauterine device or barrier methods (diaphragm, condoms, spermicides) to prevent pregnancy or practicing abstinence or where partner is sterile (e.g., vasectomy), should be considered to be of child bearing potential.

-Female subjects who are not of reproductive potential (have reached menopause or undergone hysterectomy, bilateral oophorectomy or tubal ligation) or whose male partner has undergone successful vasectomy with resulting azoospermia or has azoospermia for any other reason, are eligible without requiring the use of contraception. Acceptable documentation of menopause, sterilization, and azoospermia is patient reported history.

-All subjects must not participate in a conception process (e.g. active attempt to become pregnant or to impregnate, sperm donation, in vitro fertilization), and if participating in sexual activity that could lead to pregnancy, the female subject/male partner must use condoms (male or female) in addition to one of the following forms of contraception while on study: either a spermicidal agent, diaphragm, cervical cap, IUD, or hormonal-based contraception.

#### **EXCLUSION CRITERIA**

All candidates meeting any of the exclusion criteria at baseline will be excluded from study participation.

-Pregnancy/lactation

-Presence of inflammatory condition (besides HIV) in the last month

-Regular use of agents that may affect inflammation in the last 3 months. The regular use of NSAIDS, aspirin, or statins will be allowed as long as dose has been stable for the last 3 months and is not expected to change during the study.

-Presence of active neoplastic diseases requiring chemotherapy and/or use of immunosuppressive drugs

-Consuming supplements containing more than the DRI level of nutrients known to affect the immune response, i.e. vitamins E, C, B6, selenium, zinc, or  $\beta$  -carotene and unwilling to stop.

-BMI <18 kg/m^2.

-Known cardiovascular disease

-Uncontrolled diabetes

-Allergy or intolerance to zinc sulfate.

-Hospitalization within the previous 28 days.

- Alcohol or recreational drug use with poor history of compliance
- Inability or unwillingness of the individual to give written informed consent
- Any of the following laboratory findings obtained within 14 days prior to the screening evaluation including the following:
  - AST and ALT > 2.5 x ULN
  - Hemoglobin < 9.0 g/dL
  - GFR <50 mL/min

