### **STUDY DESIGN**

This is a double-blind randomized placebo-controlled trial, studying zinc supplementation to prevent HIV comorbidities that are linked to inflammation in subjects  $\geq 18$  years old HIV-infected patients, on stable ART (for at least 12 weeks) and with zinc levels  $\leq 0.75$  mg/L in the last 60 days. The duration of the study will be 24 weeks. The total sample size is 95 patients (n=62 on active and 31 on placebo). Patients will be randomized 2:1 to zinc gluconate tablets at a dose of 90 mg elemental zinc daily or matching placebo. For this confirmatory phase of the randomized trial, we propose twice the number of subjects in the treatment arm compared to the placebo arm from the context of feasibility, resource allocation or logistics, ethical point of view, and risk-benefit ratio. We propose to measure a number of inflammatory and immune activation biomarkers. From our prior experiences with these biomarker distributions, we may find more variability (may include outliers) in some of the response variables (biomarkers) in the treatment arm than the variability in the response variables in the placebo arm. To reduce the impact of such variability in estimating the effect sizes, having more subjects in the treatment arm should lead to more precise estimates, and hence more powerful statistical inferences. Study drugs will be provided free of charge to study participants for the duration of their participation in the study. Antiretroviral therapy will not be provided by the study. The decision for ART changes or discontinuation will be left to the primary care provider, but these changes will be documented in the study chart and will be taken into account during the analyses.

Subjects will be evaluated and data will be collected according to the following schedule:

Evaluation (Weeks)	Screen I	Screen II	Entry	6	12	18	24
Family history of CVD and diabetes		X					X
Framingham and Reynolds Risk Scores			X		X		X
Targeted physical, blood pressure, weight		X	X	X	X	X	X
Anthropometric Measurements	X	X					X
Compliance, safety monitoring				X	X	X	
Smoking, illicit drugs and alcohol status	X				X		X
Dietary and Activity status	X				X		X
Height	X						
Hematology/chemistries	X	X	X	X	X	X	X
Urine $\beta$ -HCG (women)	X	X	X	X	X	X	X
Lipoprotein profile			X		X		X

Insulin, glucose, HOMA-IR			X	X		X
Inflammation and immune activation markers			X	X		X
Gut integrity, microbial translocation, intestinal permeability			X	X		X

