#### Blinding:

Patients, study staff, and the study statistician will be blinded to treatment allocation (zinc gluconate or placebo capsules).

The research staff as well as the principle investigator will remain blinded to treatment assignment. The research staff will be responsible to prepare DSMP reports with the principal investigator and will include enrollment and dropout rates, protocol deviations, subjects symptoms, review of clinical, laboratory results and percent adherence to treatment, while remaining blinded to treatment allocation.

The principle investigator, as well as the DSMB board will remain blinded throughout the conduct of the clinical trial unless unblinding is warranted to optimize management of an adverse event or for other safety reasons. This will occur in a private location to ensure the rest of the team remains blinded.

All statistical analyses will also be done in a blinded fashion. Data will be exported to the statistician as arm A versus arm B by the research nurse to preserve blinding. For analyzing adherence, they will also only have access to the percent as opposed to pill counts the research nurse uses to calculate this.

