Zinc Supplementation: At the doses used, uncommon side effects include nausea, vomiting, and abdominal pain (gastritis). At higher doses and when used for a long periods (years), copper deficiency and related anemia may happen. This is extremely unlikely since we are only giving 90 mg daily for up to 24 weeks. Such doses have been shown to be safe even when given for 12 months to elderly frail subjects. In addition, in diseases such as Wilson's disease, zinc is given at a dose of 50 mg three times daily for prolonged durations. We will closely monitor subjects who will receive blood draws for chemistries, hematology and liver enzymes.

Cognivue test: There are no physical risks associated with completing this computerized questionnaire. The test will take about 10 - 30 minutes to complete during each visit

OTHER RISKS: Patients are informed to tell their study doctor or study nurse about all other drugs they are currently taking including non-prescription medications, alcohol, recreational, and herbal products. These drugs, if taken with the study medication, can result in dangerous interactions. If patients have questions about the drug that will be used in this study and the potential for interaction with other drugs that they take, they are instructed to ask their study doctor to provide additional information.

In addition to the risks and discomforts listed here, there may be others that are currently not known.

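### The only zinc-intolerance exclusion names zinc sulfate, but the trial gives zinc gluconate

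*Combined protocol and SAP*

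**What the plan says.** The EXCLUSION CRITERIA section opens with a binding instruction: "All candidates meeting any of the exclusion criteria at baseline will be excluded from study participation". The only item in the list about allergy or intolerance reads "Allergy or intolerance to zinc sulfate".

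The study product is described differently. Under Intervention and Duration: "Patients will be given zinc gluconate capsules at a dose of 90 mg elemental zinc daily or matching placebo for 24 weeks". Under Sample size and population: "63 patients will be randomized to two 45 mg (or 90 mg) capsules of zinc gluconate". Under STUDY DESIGN: "Patients will be randomized 2:1 to zinc gluconate tablets at a dose of 90 mg elemental zinc daily or matching placebo". Under Blinding: "Patients, study staff, and the study statistician will be blinded to treatment allocation (zinc gluconate or placebo capsules".

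The nearest inclusion criterion asks for "No diarrhea or nausea/vomiting for the last month". The RISKS AND DISCOMFORTS section says of the supplement: "At the doses used, uncommon side effects include nausea, vomiting, and abdominal pain (gastritis".

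**The concern.** An intolerance exclusion should keep out people known to react badly to what they may be given. Here it names a different salt. Followed to the letter, it gets both cases wrong: it admits someone with a documented reaction to zinc gluconate, and it excludes someone whose only reaction was to zinc sulfate.

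What is at stake is participant protection at screening. The protocol lists gastrointestinal effects, described as uncommon, at the doses used, so a past reaction to a zinc product is history that screening should capture. Safety is also part of a primary objective, and tolerability is a secondary endpoint. The rule on pre-existing intolerance at entry should therefore match the product whose tolerability is being assessed.

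**Working it through.** No power, error rate or sample size depends on this point, so the check compares the text of the relevant sections.

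**1. Which salt is the study product?**

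| Section | Salt of the assigned product |
|---|---|
| Intervention and Duration (précis) | gluconate |
| Sample size and population (précis) | gluconate |
| STUDY DESIGN | gluconate |
| Blinding | gluconate |

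That is 4 of 4 for gluconate and 0 of 4 for sulfate.

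**2. Where does zinc sulfate appear?** In two places only: the exclusion item, and a remark in BACKGROUND on its low cost and good safety record. The BACKGROUND remark does not say that sulfate will be given.

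**3. Does another exclusion cover the gap?** The list has 13 items:

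1. pregnancy or lactation
2. inflammatory condition
3. agents affecting inflammation
4. active neoplasm or immunosuppressants
5. high-dose supplements
6. low BMI
7. cardiovascular disease
8. uncontrolled diabetes
9. zinc sulfate allergy or intolerance
10. recent hospitalization
11. alcohol or drug use with poor compliance
12. no consent
13. laboratory limits

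One of the 13 concerns zinc allergy or intolerance, and it names sulfate. None names gluconate, the study drug or the capsule excipients, and none allows exclusion at the investigator's discretion. The supplement item also mentions zinc, but it is about intake above the dietary reference level in someone unwilling to stop, not about a past reaction.

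**4. Does anything outside the exclusion list cover it before dosing?**
- The inclusion criterion on gastrointestinal symptoms looks back one month only. A candidate who reacted to zinc a year ago and stopped taking it would pass.
- The screening procedures list no question about past reactions to zinc. A medical history is taken at the entry visit, but no criterion says what to do if it reveals gluconate intolerance.
- TOXICITY MANAGEMENT acts only once study drug has been taken. The criteria for permanent discontinuation govern people already in the study.

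**5. Is the dose affected?** No. Two capsules × 45 mg = 90 mg elemental zinc daily, which agrees with Intervention and Duration, BACKGROUND, STUDY DESIGN and STATISTICAL CONSIDERATIONS. The parenthetical 90 mg in the sample-size paragraph and the word tablets in STUDY DESIGN are clerical slips and carry no weight here.

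**The case against.** The best reply is that this is a slip of the pen. The purpose of the item is obvious, and an investigator running a zinc trial would very likely apply it to zinc in any form. BACKGROUND supports that reading: straight after the remark on zinc sulfate it speaks of an affordable treatment relevant to millions, as if sulfate were a loose label for the study zinc. The side effects are called uncommon, and the protocol cites safe use of this dose for 12 months in elderly people. Other safeguards exist: a medical history at entry, consent that describes the risks, symptom questions at every on-study visit, rules for holding study drug, and withdrawal at the request of the participant or primary care physician. Adding excipients to the criterion also goes beyond correcting the salt.

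Much of this stands as an argument about size. A known reaction would probably be noticed, and the likely harm is small. It does not remove the defect. None of the safeguards is an allergy exclusion, and several act only after exposure. If the broad reading is what the authors intend, the criterion should say so and not depend on each screener's interpretation. The excipient wording is an addition and not part of the error, but it is reasonable: placebo recipients also swallow capsules, the product comes from a compounding pharmacy, and the protocol lists no excipients.

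**Conclusion.** The concern holds as a minor error in an operative rule. The only zinc-intolerance exclusion names a salt that participants will not receive, and nothing else in the protocol excludes a candidate with known intolerance to the study product before dosing.

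The conclusion rests on a literal reading of the criterion; a generous reading would remove most of the practical effect. The rule is applied to every candidate for the 95 places, of whom 62 (STUDY DESIGN) or 63 (Sample size and population) are to take zinc gluconate. That is the reach of the rule and does not show how many people would be wrongly admitted. The documents give no rate of gluconate intolerance, so that number cannot be estimated and may be very small. There is no effect on dose, sample size, power or analysis.

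**What to change.** Reword the item in EXCLUSION CRITERIA to: *Allergy or intolerance to zinc gluconate, any other zinc preparation, or any excipient of the study capsules.* This keeps the present sulfate exclusion and closes the gap for the product given.

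Two clerical edits can go in the same amendment. In Sample size and population, state two capsules daily, each with 45 mg elemental zinc as zinc gluconate, for a total of 90 mg per day. In STUDY DESIGN, change tablets to capsules.

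The cost is one reworded criterion and two wording corrections at the next amendment, with no added visits, tests or procedures.
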